3.1 Inclusion Criteria

- 1. Patients with symptomatic, diagnostically confirmed COVID-19, per RT-PCR or antigen assay of respiratory tract sample.
- 2. Patient must have either become symptomatic or found positive by RT-PCR or antigen assay within 5 days, whichever is greater, of randomization.
- Patients must have at least two symptoms of at least moderate severity on initial questionnaire. Fatigue, anosmia, ageusia or dysgeusia may not be counted among the symptoms of at least moderate severity qualifying the patient for entry,

Note: patients should NOT be informed prior to completion of the questionnaire that presence of at least 2 symptoms of moderate severity is a criterion for study entry.

- 4. Males and females ≥age 18 years.
- 5. Oxygen saturation by pulse oximeter ≥92% on room air.
- 6. Negative urine or serum pregnancy test (if woman of childbearing potential).
- 7. Females of childbearing potential and males with female partners of childbearing potential must agree to use acceptable contraceptive methods during the study and for at least two months after the last dose of study medication.
- 8. The patient must be able to complete the diary independently at baseline.
- 9. The patient give informed consent based on an IRB-approved consent form.

3.2 Exclusion Criteria

- 1. Patient is in need of acute hospitalization per clinician assessment.
- 2. Pregnant or nursing women.
- 3. Unwillingness or inability to comply with procedures required in this protocol.
- 4. Patient requires supplemental oxygen.
- 5. Patient is currently receiving, has received within the past 7 days or is expected to receive during the course of the study remdesivir, or other specific antiviral or anticytokine therapy for COVID-19, other than therapeutic monoclonal antibodies allowed or approved in the region in which the patient lives, or systemic corticosteroid equivalent to ≥20 mg daily prednisone/3 mg dexamethasone daily.
- 6. Patient is currently receiving or has received within 30 days prior to screening any other investigational agent for any indication, including approved agents given for investigational indications (e.g., anti-cytokine treatments).
- 7. Patient is currently taking or is expected to start taking warfarin, apixaban (Eliquis), or rivaroxaban (Xarelto). Patients may be taking or start on study dabigatran (Pradaxa), standard or low molecular weight heparin.

CONFIDENTIAL: PROPRIETARY INFORMATION

4. Study Design

4.1 Overview

This is a randomized, parallel-group double blind study of upamostat compared to placebo in patients with symptomatic COVID-19 who do not require immediate treatment with specific antiviral or anticytokine therapy. The study uses phase 2/3 operationally seamless design methodology for dose selection in phase 2 (part A) and inferentially independent confirmatory phase 3 study (part B). The phase 3 portion will include interim analysis for early termination for futility or increase in sample size, as indicated by initial results.

In both parts of the study, patients who have a positive PCR or rapid antigen test for SARS-CoV-2 and meet inclusion and exclusion criteria will be stratified by age (≥65 vs <65 years). In part B, they will also be stratified based on presence of one or more concerning medical conditions and the additional factors shown below and then randomized to treatment with upamostat or placebo, according to randomization ratios specified below. Concerning medical conditions are the following:

- Age ≥65 years on date of randomization
- Hypertension
- Chronic lung disease (for example, chronic obstructive pulmonary disease, moderate-severe asthma, interstitial lung disease, cystic fibrosis and pulmonary hypertension) Diabetes
- Obesity (BMI≥30)
- Cardiovascular disease (including congenital heart disease, coronary artery disease, history of thrombotic events, including stroke and transient ischemic attacks [TIA])
- Chronic renal disease
- Immunosuppressive disease or immunosuppressive treatment
- Sickle cell disease
- Neurodevelopmental disorders (for example, cerebral palsy) or other conditions that confer medical complexity (for example, genetic or metabolic syndromes and severe congenital anomalies)
- Having a medical-related technological dependence (for example, tracheostomy, gastrostomy, or positive pressure ventilation (not related to COVID-19))

All patients who live in regions in which one or more therapeutic monoclonal antibody combinations for outpatient treatment of COVID-19 are available will either be offered antibody, if provided at that facility, or given information as to where they can receive the antibodies. The patient may decide whether or not to take the antibody combination; receipt or refusal of antibody therapy will not affect the patient's participation in this trial. If used, the antibody may be administered before or after the patient starts study medication. However, the patient may not start study medication more than 5 days after onset of symptoms or receipt of laboratory diagnosis of COVID-19, whichever is longer.

In part B, patients will be stratified based on

- 1. The presence of none versus one or more of the above factors,
- Planned receipt vs nonreceipt of therapeutic monoclonal antibodies for COVID-19,
- 3. Region in which patient is treated,

4. Whether the patient is at least 14 days after his or her last dose of COVID-19 vaccine.

and randomized to treatment as described below.

Initially in part B, the proportion of patients in the low risk group, i.e., with no concerning conditions, will be limited to 30%. This number and the definition of high risk, in terms of number and types of risk factors, may be revised at the time of the part A analysis and, in order to enroll a very high risk cohort, again at the interim analysis in part B.

Part A

Initially, a total of 60 patients will be randomized to one of three treatment groups, as follows:

- 1. Upamostat 200 mg two capsules qd (n=20);
- 2. Upamostat 200 mg one capsule and matching placebo one capsule qd (n=20)
- 3. Placebo two capsules qd (n=20).

In order to maintain blinding, patients will be given two bottles of medication and instructed to take one pill from each bottle each day. Both pills are to be taken at the same time.

Part B

After all part A subjects complete the study, further randomization into the study will be held until the part B dose regimen is selected and the high risk or very high risk population is further defined. Analysis of part A will be performed by a data and safety monitoring board (DSMB). Assuming that there are no substantive negative safety signals to continuing with at least one dose level, a decision will be made regarding continuing with the current design and sample size or increasing the number of patients in part B to enable detection of a significant improvement in the incidence of hospitalization or death in the upamostat group as compared to placebo.

If the decision is to continue as originally planned, an additional total of 250 patients, will be treated with the dose selected in part A or placebo. If the decision is to power for detection of a significant effect on hospitalization or death, the sample size will be increased in accordance with the power calculations to be performed at that time.

The DSMB decision-making process is further defined in section 4.7 of the protocol, below, and will be detailed in a separate DSMB charter. As the results of part A will not be combined with those of part B, the analyses may be shared with the sponsor and study team.

Based on results from part A, a dose for part B, either 200 mg (one capsule) or 400 mg (two capsules) daily will be selected. Patients will then be randomized 3:2 to active drug or placebo at the schedule selected based on part A. If the study is powered for the symptom resolution endpoint, part B will have an event-driven design, requiring total of 201 endpoint-events (details in Section 7.1) The target sample size for this part is 250 patients, 150 receiving active drug and 100 receiving placebo. An interim analysis for early termination for futility or increase in sample size (up to maximum total 375), as indicated by comparative interim results will be performed after 50% of the primary endpoint recovery events are realized (details in section 4.8 and section 7.6). This interim analysis is estimated to occur when about 50% (125) of part B subjects have been enrolled and treated.

If the study is repowered to demonstrate a significant reduction in hospitalization or death, the timing of the part B interim analysis may be revised. At the interim analysis, the incidence of hospitalization or death as a function of presence of concerning conditions will be assessed and the stratification or covariate weighting for the final analysis may be modified based on this analysis. In addition, the sample size may be increased by 50% depending on results of the interim analysis.

4.2 Study Drug Administration

4.2.1 Upamostat

Upamostat will be administered as one or two 200 mg capsules once daily for 14 days, preferably at approximately the same time each day. Medication should be administered with water and may be administered with or without food.

4.2.2 Placebo

Placebo will be administered as described above.

4.2.3 Dose modifications

Toxicity is an adverse event judged by the investigator to be possibly, probably or definitely related to study medication. All grade 1 toxicities and adverse events and tolerable unrelated grade 2 adverse events can be treated according to standard clinical practice guidelines, without dose modification.

See Table 2 for the Dose Modification Plan for patients experiencing ≥grade 2 toxicities.

Table 2. Dose Modification Plan for Treatment-Related Toxicities

NCI CTC 5.0 Criteria	Dose Modification Instructions		
Symptomatic toxicity (e.g., nausea, vomiting or diarrhea) or laboratory abnormalities (e.g, hypokalemia) ≥grade 3 which can be reduced to ≤grade 1 within 48 h with standard supportive measures	No dose modification.		
Any intolerable grade 2 toxicity	The investigator should consult the study sponsor regarding grade 2 toxicities that are considered intolerable by the patient or physician. A dose reduction may occur with prior consultation with and approval by the study sponsor.		
Any toxicity ≥grade 3 other than the	Hold study drug.		
above	Assess patient at least every 3 days.		
	If the toxicity improves to ≤ baseline within a week, restart study drug and reduce dose by one dose level (Table 3).		
	If toxicity does not improve to ≤ baseline within one week, discontinue study drug.		
	Omitted doses are not made up.		

CONFIDENTIAL: PROPRIETARY INFORMATION

Patients may undergo two step-wise dose reductions, as shown in Table 3. Only two dose reductions are allowed. If the patient still has significant toxicity, as described in Table 2, after two dose reductions, treatment is to be stopped.

Table 3. Dose Levels

Dose Level		
Starting dose	1 cap daily	2 caps qd
Reduction 1	1 cap q2 days	1 cap qd
Reduction 2	Discontinue	1 cap q2 days

In part A of the study, patients may get two bottles of capsules with the same drug (active or placebo) or one bottle of each, active and placebo. In order to dose reduce in that situation, the patient will be told to take one capsule from alternate bottles on alternate days, stopping at day 15, regardless of how many capsules are left. Generally, one capsule should remain at the end of the study, unless a capsule was accidentally damaged or lost.

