4.8 Data and Safety Monitoring Board

A data and safety monitoring board (DSMB) will be convened for oversight of the study. A DSMB charter will be written as a separate document.

Preliminary review: The DSMB will be informed by the Sponsor on an ongoing basis of each patient whose study medication dose is reduced or discontinued due to toxicity. DSMB members may request an early review of all patients if warranted by the type, severity or frequency of toxicities resulting in dose reduction or drug discontinuation.

Initial full review: The DSMB will review data after the 60 patients have completed treatment (part A), with regard to the following:

- a) Adverse events requiring dose modification or discontinuation of treatment overall and those considered at least possibly related to study medication;
- b) Serious adverse events deemed at least possibly related to study medication;
- c) Serious adverse events of any cause;
- d) Exacerbation of COVID-19 disease, including hospitalization or death;
- e) Effect of treatment on oxygen saturation, C-reactive protein, lymphocyte count and D-dimer (pharmacodynamic markers);
- f) Additional efficacy parameters available at that time, including time to sustained recovery
- g) Correlations between comorbidities and hospitalization or death.

A statistically significant difference in any of these parameters is unlikely with a limited early data set. However, the DSMB in conjunction with the sponsor will determine using their clinical judgement if, based on the safety profile of the two active arms, the tolerability is substantially lower at 400 mg as compared to 200 mg daily.

- A. If the DSMB determines that safety of both dose levels is similar, accrual in part B will proceed with the 400 mg daily schedule.
- B. If safety is more favorable with the 200 mg daily regimen, accrual in part B will proceed with the 200 mg daily schedule.

Efficacy will be analyzed in part A but, unless there is a marked difference between the two active dose levels, will not be used to decide on dosing in part B. Similarly, pharmacodynamic parameters will be analyzed but not used to decide on dosing.

At the end of part A, incidence of hospitalization or death will be analyzed as a function of the presence of one or more concerning conditions. The definition of high risk for purposes of the hospitalization/mortality endpoint in part B may be adjusted based on findings in part A.

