For part A of the study, the two bottles provided will be labeled A and B. Patients will be instructed to take one capsule from each bottle each day. For patients in the 200 mg daily group, i.e., receiving different medications in bottles A and B, active and placebo will be randomized between the two bottles so that A or B will not automatically signify either active or placebo. If dose is reduced, patients will be instructed to take one pill from alternate bottles each day.

9. Investigator Responsibilities

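### Part A dose reduction: the first step works blind, but the second step, the bottle wording, the number of reductions and the leftover-capsule figure do not agree with one another

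*Protocol*

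**What the plan says.** Protocol 4.1 sets three part A arms of 20: two active capsules (400 mg), one active plus one placebo capsule (200 mg), and two placebo capsules. To keep the blind, all patients get two bottles and are "instructed to take one pill from each bottle each day".

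Protocol 4.2.3, Table 3, has two columns, headed by the row "Starting dose 1 cap daily 2 caps qd". The one-capsule column goes to one capsule every two days and then to discontinuation. The two-capsule column goes to one capsule daily and then to one capsule every two days. The text above the table says: "Patients may undergo two step-wise dose reductions, as shown in Table 3. Only two dose reductions are allowed".

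Two places turn this into bottle instructions for part A. Section 4.2.3 says that "the patient will be told to take one capsule from alternate bottles on alternate days, stopping at day 15". Section 8 (Study Medications) says: "If dose is reduced, patients will be instructed to take one pill from alternate bottles each day". Neither separates a first from a second reduction. Section 4.2.3 then adds: "Generally, one capsule should remain at the end of the study, unless a capsule was accidentally damaged or lost". Section 8 promises a 14-day supply but does not give the number of capsules per bottle.

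The first item that the DSMB reviews at the end of part A (Protocol 4.8, repeated in SAP Section 7) is "Adverse events requiring dose modification or discontinuation of treatment overall and those considered at least possibly related to study medication". SAP Section 15 tabulates AEs leading to discontinuation separately from those leading to dose modification. SAP Section 11 lists and summarises planned and actual mg/day by study day and arm.

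**The concern.** A blinded site sees two capsules a day in every patient. Table 3 sorts patients by a starting dose of one or two capsules, and its columns part at the second reduction, where one stops and the other goes on. It is not clear which column a 200 mg patient belongs to, since this patient swallows two capsules but takes one active one. The two bottle instructions are also worded differently, and the check figure on leftover capsules looks hard to reach.

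At stake is the comparison of 200 mg with 400 mg that decides the part B dose. If the same toxicity course ends as a discontinuation in one arm and as a further reduction in the other because of how the table is read, part of any difference comes from the rule and not from the drug. The one-capsule column also matters in part B if 200 mg is chosen, because patients would then take one capsule daily (Protocol 4.3).

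**Working it through.** **Inputs.** Capsule strength is 200 mg (Protocol 4.2.1). The arms are those of Protocol 4.1, the steps those of Table 3, and the bottle instructions those of 4.2.3 and 8. There are 14 dosing days (4.2.1; Table 1, footnote a, puts the end-of-treatment visit on the day after the last dose). Capsules per bottle are not given, so I assume 14 and also show 15. The plan has no calculation of its own here to reproduce.

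**Step 1: average active dose under each schedule.**

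| Schedule in part A | 400 mg arm | 200 mg arm | Placebo |
|---|---|---|---|
| Full dose, one from each bottle daily | 400 mg/day | 200 mg/day | 0 |
| One capsule daily, bottles alternating | 200 mg/day | 200 mg every 2nd day = 100 mg/day | 0 |
| One capsule every 2nd day, bottles alternating | 200 mg every 2nd day = 100 mg/day | 200 mg every 4th day = 50 mg/day | 0 |

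**Step 2: compare with Table 3 in active dose.** The one-capsule column is 200 mg/day, then 200 mg every second day, then stop. The two-capsule column is 400 mg/day, then 200 mg/day, then 200 mg every second day. The second row of the table above equals Reduction 1 in both columns, so the first reduction needs no knowledge of the arm.

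**Step 3: the second reduction.** There are two readings of the columns.
- Active dose: the 200 mg arm discontinues and the 400 mg arm goes to one capsule every two days. A blinded site cannot tell which applies.
- Capsules swallowed: every part A patient follows the two-capsule column and the blind holds. The 200 mg arm then receives 200 mg every fourth day, which appears nowhere in Table 3.

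On either reading, no bottle instruction describes this step.

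**Step 4: the two bottle instructions.** Section 8 gives 200 and 100 mg/day (400 and 200 mg arms). Section 4.2.3 gives the same if it means bottle A one day and bottle B the next. If it means a capsule only on alternate days, it gives 100 and 50 mg/day. The ratio is 200/100 = 100/50 = 2. On that second reading a 400 mg patient goes straight to the Reduction 2 level.

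**Step 5: number of reductions.** The text allows two reductions without regard to starting dose. The one-capsule column holds one reduced dose and then a stop.

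**Step 6: leftover capsules.** Let k be the number of full-dose days before reduction.
- 14 per bottle, no hold, one daily: 28 − 2k − (14 − k) = 14 − k. At k = 7 this is 7. It is 1 only at k = 13, when reduction starts on the last dosing day.
- 14 per bottle, no hold, one every second day: 28 − 2k − (14 − k)/2, with the last term rounded up. At k = 7 this is 28 − 14 − 4 = 10. At k = 13 it is 28 − 26 − 1 = 1, and at k = 12 it is 28 − 24 − 1 = 3.
- 15 per bottle: both counts rise by 2, so the smallest remainder is 3.
- One daily after a hold of h days (1 to 7), 14 per bottle: 28 − 2k − (14 − k − h) = 14 − k + h. At least one reduced-dose day requires k + h ≤ 13, so the smallest value is 14 − 12 + 1 = 3 and the largest 14 − 1 + 7 = 20. With 15 per bottle the range is 5 to 22.

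Table 2 requires a hold before restarting at a lower dose for most toxicities of grade 3 or above, so the hold case is the usual one on that route.

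**The case against.** The strongest reply is that Table 3 is written in capsules, not milligrams. Every part A patient takes two capsules, so part A uses the two-capsule column throughout, and the one-capsule column is there for part B at 200 mg. Alternating the bottles is itself the blinding device. On this reading nothing depends on the hidden arm, and a claim that the reduction rules as a whole cannot be applied blind would be wrong. That much stands: it is plainly wrong for the first reduction. What the reply leaves open is that the protocol does not say which reading is meant, that the second step then puts the 200 mg arm on an unlisted level, and that this step has no bottle instruction.

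A reader might also infer that the two bottle instructions contradict each other. On the most natural reading of 4.2.3 they agree. The twofold gap arises only on the other reading, so this is an ambiguity and not a demonstrated conflict.

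A third point is that the number of reductions is partly a matter of labels, since Table 3 calls the stop in the one-capsule column Reduction 2. That softens the conflict without removing it, because a stop is not a reduced dose.

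A reader might further infer that the dose-selection data are distorted. The documents do not show this. The Table 2 triggers are the same in all arms. The DSMB item pools modification with discontinuation, so a patient needing a second step already counts there from the first. The choice also rests on serious adverse events and clinical judgement, and nothing tells sites to unblind in order to find a column.

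Finally, a reader might think that the leftover figure would mark correctly dosed patients as non-adherent. It would not: SAP Table 2 judges missed treatment days and exempts investigator-directed reductions and holds, and no analysis uses capsule counts.

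**Conclusion.** The part A dose-reduction text is internally inconsistent, within limits. The first reduction is sound. The second cannot be carried out as written under blind without either knowing the arm or leaving Table 3. The 4.2.3 bottle wording admits a reading at half the Section 8 dose, the allowance of two reductions disagrees with the one-capsule column, and the leftover figure is right only in a corner case. The leftover conclusion rests on 14 dosing days and an assumed 14 or 15 capsules per bottle.

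The effect on the tolerability comparison is possible but cannot be sized. It is confined to patients who need a second step within 14 days or who are dosed under the other reading, and the documents give no rate for either. It would show in the SAP's separate tables of AEs leading to discontinuation and to dose modification, and in planned mg/day, which is not settled for the 200 mg arm after a second reduction. For scale only, one patient in an arm of 20 is 1/20 = 5 percentage points; that is not a forecast that any patient would be reclassified.

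**What to change.** Reconcile Protocol 4.2.3 (text, Table 3 and leftover count) with Section 8:
- State whether the Table 3 columns mean capsules taken or active dose.
- Write each part A step, including the second, in terms that a blinded site can carry out without knowing the arm.
- Use one wording for the bottle instruction in both sections.
- Make the stated number of reductions agree with both columns, which also settles the rule for part B if 200 mg is chosen.
- Correct or delete the leftover-capsule figure.

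Which schedule is intended is for the sponsor to decide. The planned mg/day in SAP Section 11 should then follow from it.

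The cost is a protocol clarification and a site memo, with no new data or patients. Sites that have already reduced a patient under another reading would need retraining.
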